**Abstract**

The use of d-cycloserine (DCS) as a cognitive enhancer to augment exposure-based cognitive- behavioral therapy (CBT) represents a promising new translational research direction with the goal to accelerate and optimize treatment response for anxiety disorders. Some studies suggest that DCS may not only augment extinction learning but could also facilitate fear memory reconsolidation. Therefore, the effect of DCS may depend on fear levels reported at the end of exposure sessions. This paper presents the rationale and design for an ongoing randomized controlled trial examining the relative efficacy of tailoring DCS administration based on exposure success (i.e. end fear levels) during a 5-session group CBT protocol for social anxiety disorder ( $n = 156$ ). Specifically, tailored post-session DCS administration will be compared against untailored post-session DCS, untailored pre-session DCS, and pill placebo in terms of reduction in social anxiety symptoms and responder status. In addition, a subset of participants ( $n = 96$ ) will undergo a fear extinction retention experiment prior to the clinical trial in which they will be randomly assigned to receive either DCS or placebo prior to extinguishing a conditioned fear. The results from this experimental paradigm will clarify the mechanism of the effects of DCS on exposure procedures. This study aims to serve as the first step toward developing an algorithm for the personalized use of DCS during CBT for social anxiety disorder, with the ultimate goal of optimizing treatment outcome for anxiety disorders.

## Introduction

Whereas ample evidence supports the efficacy of cognitive behavioral therapy (CBT) for anxiety disorders, response rates leave considerable room for improvement. Attempts to improve treatment response with combined CBT and anxiolytic pharmacotherapy have led to disappointing results. One promising strategy for strengthening the effects of CBT has been the use of pharmacological agents that augment core learning processes in CBT. One important element in CBT for anxiety disorders is exposure procedures, which rely on extinction learning. Preclinical research has shown that extinction learning is blocked by antagonists at the glutamatergic N-methyl-D-aspartate (NMDA) receptor, whereas d-cycloserine (DCS), a partial NMDA agonist, augments such learning in animals.

In clinical settings, a number of studies have shown that DCS also appears to augment the effects of exposure therapy. In one of the first human trials, patients with social anxiety disorder (SAD) who received 50 mg of DCS one hour prior to each of five exposure sessions had greater reductions in social anxiety symptoms at post-treatment and one-month follow-up than those who received exposure therapy plus pill placebo. Findings were replicated by Guastella and colleagues. Similarly, promising results were reported in the treatment of height phobia and panic disorder. In contrast, a number of studies have found minimal to no benefits for DCS augmentation of exposure procedures for various clinical and subclinical anxiety problems. In the largest DCS trial to date ( $n = 169$ ), patients with SAD showed a significantly faster rate of symptom improvement than those receiving placebo, but no differences were observed in the response or remission rates at post-treatment and 6-month follow-up. In addition to within-session changes, between session fear reduction also appears to be of importance, as shown in a recent trial with Iraq and Afghanistan veterans. After six sessions of virtual reality exposure therapy, participants showed a greater reduction in PTSD symptoms with d-cycloserine augmentation when extinction learning was well achieved between sessions, which was quantified as the average decrease in peak subjective distress ratings across successive exposure sessions. This effect was not observed when the exposure sessions were combined with alprazolam or placebo.

One possible explanation for these inconsistent findings is related to the extent to which extinction learning has occurred. Consistent with this hypothesis are the results of a re-analysis of the study by Hofmann and colleagues. The results demonstrated that relative to placebo, patients receiving DCS showed greater symptom improvement at each session when self-reported fear levels were low at the end of the prior exposure session. Conversely, patients who received DCS and whose end fear levels were high at the prior session showed less symptom improvement than those taking placebo. At post-treatment, patients receiving DCS whose average fear level at the end of each exposure was low to moderate showed superior outcome to those receiving placebo. Similar results were found in another trial with height phobic patients in which DCS was administered post-session.

It may then be best to selectively administer DCS only after exposures in which end fear levels are low, as DCS can make “good” exposures better and “bad” exposure worse. This is based on findings from animal studies suggesting that NMDA antagonists impair reconsolidation of fear memories, whereas DCS appears to enhance reconsolidation of fear memory. A critical condition determining whether DCS augments extinction learning or reconsolidation appears to be the length of memory reactivation and extinction training sessions. If the extinction session (and the period of stimulus re-exposure) is brief, reconsolidation processes are dominant, whereas extinction processes dominate in longer sessions. Therefore, if fear does not sufficiently decrease during exposure therapy, fear memory reconsolidation may occur and DCS can facilitate this counter-therapeutic process. To test the hypothesis that success of DCS depends on the level of fear experienced at the end of exposure, the present study will examine the effect of selectively administering DCS to patients after exposures in which end fear levels are low.

## Methods

### Study Design and Objectives

The primary objective of this study is to optimize the application of DCS to augment exposure therapy. We will examine the relative efficacy of tailoring post-session administration of DCS based on end fear levels during a five-session exposure therapy protocol for SAD. Tailored post-session DCS administration will be compared to the most common application of DCS in prior research, which is unselective DCS administration before exposure sessions, as well as unselective post-session DCS administration in order to determine whether post-session DCS administration needs to be tailored. We will also include a placebo condition. We hypothesize that selectively administering DCS when fear levels are low at the end of exposures will lead to greater reductions in social anxiety symptoms at post-treatment and follow-up compared to placebo, unselective pre-session DCS administration, and unselective post-session DCS administration.

A secondary aim is to examine whether DCS enhances fear extinction retention in a laboratory setting. Doing so will allow us to make inferences about the mechanism of action through which DCS enhances outcomes (i.e. whether its effects are due to increased fear extinction retention), and to better interpret any possible null results of the clinical trial (e.g. DCS may work in an experimental paradigm but not in a clinical setting). To examine the effect of DCS on fear extinction retention, a subset of participants will complete a computerized protocol involving a fear conditioning procedure, fear extinction training, and fear extinction retention testing on three separate days, while receiving DCS or pill placebo prior to extinction training. We hypothesize that participants receiving DCS will show greater fear extinction retention in the laboratory experiment than those receiving placebo.

### Participants

Our sample will consist of 156 participants for the clinical trial portion of the study, with a subset of 96 participants completing the optional laboratory-based fear extinction paradigm. Recruitment will be split amongst the three study sites: Boston University, University of Texas at Austin, and Rush University Medical Center. Inclusion and exclusion criteria are listed in Table 1.

**Table 1**

Inclusion Criteria
Primary diagnosis of SAD a
LSAS total score $\geq 60^b$
Age $\geq 18$
Medical clearance c
Willingness and ability to participate in the informed consent process/study protocol
Exclusion Criteria
Lifetime history of bipolar or psychotic disorders or obsessive-compulsive disorder
An eating disorder, PTSD, or substance abuse or dependence (other than nicotine) in the past 6 months
Organic brain syndrome, mental retardation or other potentially interfering cognitive dysfunction
History of head trauma causing loss of consciousness, seizure or ongoing cognitive impairment
Significant suicidal ideation or suicidal behaviors within 6 months prior to intake
Significant personality dysfunction likely to interfere with study participation (e.g., being overly aggressive or abusive towards the therapists or group members)
Currently pregnant or lactating, or women of childbearing potential who are not using medically accepted forms of contraception
serious medical illness or instability for which hospitalization may be likely within the next year
Concurrent psychotropic medication (e.g., antidepressants, anxiolytics, beta blockers) within the 2 weeks prior to initiation of treatment
Concurrent psychotherapy initiated within 3 months of baseline, or ongoing psychotherapy of any duration directed specifically toward treatment of the SAD
prior non-response to adequately-delivered exposure therapy

aPrimary diagnosis of SAD as defined by DSM-5 criteria

bLiebowitz Social Anxiety Scale (LSAS)

cPhysical examination and laboratory findings without clinically significant abnormalities

## **Screening and Randomization**

Individuals interested in the study will undergo a psychiatric evaluation to evaluate psychiatric inclusion and exclusion criteria. Participants will be medically cleared by a study physician.

Participants in the optional fear extinction retention experiment will be randomized to receive either DCS or placebo prior to fear extinction procedures. For the clinical trial portion of the study, participants will be randomized to one of four conditions: 1) tailored post-session DCS, 2) unselective pre-session DCS, 3) unselective post-session DCS, or 4) pill placebo. The conditions of the fear extinction experiment will be equally distributed across the four clinical trial conditions such that participants will be equally likely to receive any combination of fear extinction condition and trial condition. Randomization will occur by site using variable-sized permuted block randomization (block sizes varying from 4 to 12). Randomization tables will be created before the first subject is run and sent to the study pharmacist to make the appropriate medication kits. The statistician will check the balance of randomization to control for any unbalanced factors.

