## **Fear Extinction Retention Experiment**

The fear extinction retention experiment will occur on three separate days prior to treatment. Participants will undergo conditioning procedures on Day 1, extinction learning on Day 2, and extinction recall and fear renewal on Day 3. Day 1 and Day 3 sessions will take place no more than seven days apart. DCS or placebo will be administered immediately prior to the Day 2 procedures to examine whether DCS enhances extinction recall and reduces fear renewal on Day 3.

Experiment procedures are based on a previously validated fear conditioning and extinction paradigm. During each portion of the experiment, recording electrodes will be attached to the palm of the participant's left hand to measure skin conductance response (SCR), and stimulating electrodes will be connected to two fingers of the participant's right hand to deliver an electric shock. SCR will be measured through a 9-mm (sensor diameter) Sensor Medics Ag/AgCl electrodes. For each trial, participants will view a computer monitor with an image of one of two different rooms containing an unlit lamp for 6 seconds. The lamp will then be "switched on" to one of two colors for 12 seconds, which will serve as the conditioned stimulus (CS). One of the two colors will be paired with an electric shock (the unconditioned stimulus, or US), while the other color will not. The shock will have been previously selected by the participant to be "highly annoying but not painful" and delivered for 500 millisecond through electrodes attached to the second and third finger of the right hand. The inter-trial interval will last an average of 15 seconds. The stimulating electrodes will remain attached to the fingertips throughout the experiment, but the US will be administered only during the Conditioning session on Day 1.

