### Pill Administration

Following prior research demonstrating DCS to augment exposure therapy, DCS will be administered in 50 mg doses. Administration of DCS at such a dose has been shown to have a benign side effect profile, and increasing the dose to as high as 500 mg has not shown additive effect in enhancing exposure-based treatment. DCS and placebo capsules will be identical in appearance and administered by staff blind to study condition and not involved in the assessment or treatment of participants. Participants in the fear extinction retention experiment will take one study pill (i.e., 50 mg DCS or placebo) immediately before Day 2 of the experiment.

The pharmacist will fill three bottles (with one pill type in each) for each patient for each exposure session according to the schedule in Table 2. Patient, therapist, and staff will be blind to the drug condition (DCS vs. placebo) at pre-exposure; and therapists and patients will be blind to the drug condition at post-exposure. Regardless of study condition, research staff will administer a pill (Pill 1) to each participant one-hour before the exposure session and administer a second pill (Pill 2) immediately after the exposure session. In the tailored administration condition, the selection of Pill 2 will be guided by the end fear level. Specifically, DCS will be administered if the end fear is  $\leq 40$  (of 100) on the Subjective Units of Distress Scale (SUDS), whereas placebo will be selected if the end fear is  $> 40$ . A cutoff of 40 and below was selected based on results of our prior clinical trial, which demonstrated that when end SUDS ratings were below 47, DCS showed an advantage over placebo. Two prior studies using the same 5-session CBT protocol found that mean end SUDS ratings were 49.5 ( $SD = 19.2$ ) and 39.1 ( $SD = 17.7$ ). In the latter study, 85% of patients had at least one end SUDS rating of 40 or below, and 67.5% had at least 2 end SUDS ratings of 40 or below, demonstrating that there is sufficient variability in end fear ratings to justify the examination of tailored and non-tailored post-session DCS administration.

Pill administration schedule

Table 2

Condition	Pre-exposure (1 st Pill)	Post-exposure (2 nd Pill)	
		If SUDS $\leq 40$	If SUDS $> 40$
1. Pre-session DCS	DCS	PBO	PBO
2. Placebo	PBO	PBO	PBO
3. Non-tailored post-session DCS	PBO	DCS	DCS

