## Data Analysis

We will assess the equivalence of the treatment groups on key baseline variables and any variables that differ among groups will be used as covariates in the final analyses. We will examine missing data patterns, dropout rates, and distributional properties of measures and use transformations to improve distributions if necessary. We will use pattern mixture modeling to assess the effect of missing data. We will rerun our analyses coding for various missing data patterns (no missing data, sporadic

missing, dropouts, etc.) to determine 1) if missingness impacts our findings and 2) how the differences between treatment conditions depends on the missing data pattern.

We will use multilevel modeling (MLM) to evaluate the effect of condition on our continuous outcome measures (LSAS, SPD-SC severity, MADRS, QLES-Q) and generalized linear mixed modeling (GLMM, which is MLM with a logistic linking function) to examine DCS's effect on the dichotomous outcomes ("response" and "remission," explained below). MLM is the recommended method for analyzing longitudinal psychiatric data, easily accommodates missing data, and allows inclusion of all subjects in the analysis even if they drop out. In our MLM analyses, the repeated assessments over time will be nested within individuals, which will be nested within treatment cohort, thereby appropriately accounting for correlated scores within cohorts. We will use a piecewise growth curve model, separately modeling change over time during treatment and follow-up. We will test for quadratic trends and include them if significant. Other non-linear models (e.g., exponential models) will be also be tested, and the model that best fits the data (based on AIC and BIC) will be used. Our "time" variable in these models will be coded as "assessment week" and will reflect the number of weeks since baseline. Using this model, we can test differences between tailored DCS administration and the 3 comparison groups (pre-session DCS, post-session DCS, and placebo) by including 3 dummy coded variables as predictors of the growth curve parameters. Each dummy variable will contrast tailored DCS to each of the other 3 conditions.

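### The clinical model omits the laboratory drug assignment that the design crosses with the four arms, so no stated analysis examines whether laboratory DCS affects clinical outcome

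*Combined protocol and SAP*

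**What the plan says.** The Participants section sets 156 participants for the clinical trial, 96 of whom also complete the optional laboratory experiment. Under Fear Extinction Retention Experiment, "The fear extinction retention experiment will occur on three separate days prior to treatment". Those who take part "will be randomized to receive either DCS or placebo prior to fear extinction procedures", and under Pill Administration they "will take one study pill (i.e., 50 mg DCS or placebo) immediately before Day 2 of the experiment", the same DCS dose as in the trial. A limit is set on the time from Day 1 to Day 3, but no minimum interval between the laboratory dose and the first treatment session is stated.

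For the clinical trial, "participants will be randomized to one of four conditions". The two assignments are deliberately crossed: "participants will be equally likely to receive any combination of fear extinction condition and trial condition". Randomisation is by site in permuted blocks, with "block sizes varying from 4 to 12".

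Data Analysis tests condition by "including 3 dummy coded variables as predictors of the growth curve parameters", each comparing tailored DCS with one other arm. Further covariates enter only if a key baseline variable differs among the groups. Screening and Randomization adds that the statistician will control for factors found to be unbalanced. Laboratory assignment is not named as a covariate, stratum or moderator. The moderator families given as examples in Outcome Analysis are demographic, clinical and personality characteristics.

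**The concern.** The design creates a randomised factor that precedes the clinical outcome, and the clinical analysis then does not use it. The two rules that could bring it in are triggered by a difference between groups, and a factor balanced by design would normally trigger neither.

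The introduction argues that the effect of DCS depends on the learning it accompanies, so it is a fair question whether one earlier dose, paired with extinction training, alters the response to later exposure sessions. The laboratory arm is also meant to help interpret a null clinical result. A null difference between tailored DCS and placebo is harder to read if nobody has checked whether laboratory DCS moved the clinical scores, given that about three in ten placebo patients will have had it.

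**Working it through.** **Inputs.** 156 in the trial, 96 in the experiment (Participants); four arms and two laboratory conditions, crossed (Screening and Randomization); detectable effect d = .296, or 6.59 LSAS points, at power .80 (Power analysis). Assumed, because not stated: equal allocation to arms and a two-sided 0.05 test.

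**The plan's own figure.** The d of .296 cannot be reproduced, because the variances and covariances given to PinT are not printed. It implies an LSAS SD of 6.59/.296 = 22.3. Single-measurement formulas give .634 for 39 v 39, .518 for 39 v 117 and .449 for 78 v 78, but they ignore the repeated measures. I use 6.59 points only as a yardstick, taken as the detectable difference for one 39 v 39 contrast. The omission itself does not depend on it.

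**Expected counts.**
- Per arm: 156/4 = 39.
- Per arm in the experiment: 96/4 = 24.
- Per combination: 96/(2 × 4) = 12, so 12/39 = 30.8% of each arm is on laboratory DCS.

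**Effect on tailored minus placebo.** With carry-over c_T in the tailored arm and c_P in placebo, bias = (12/39) × (c_T − c_P).
- Equal carry-over: (12/39)c − (12/39)c = 0.
- Carry-over in placebo only (an illustrative worst case): the contrast loses 0.308 × c_P. The standard error implied by 6.59 points at power .80 is 6.59/2.80 = 2.35, and power = Φ(effect/2.35 − 1.96).

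| Carry-over in placebo only, as a share of 6.59 | Contrast left (LSAS points) | Power |
|---|---|---|
| 0 | 6.59 | .80 |
| 25% | 6.08 | .73 |
| 50% | 5.58 | .66 |
| 100% | 4.56 | .49 |

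No row beyond the first is supported by a figure in the documents.

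**Chance imbalance.** If laboratory assignment were not balanced across arms, a hypergeometric draw (48 laboratory-DCS patients among 156, 39 per arm) gives a 95% range of about 7 to 17 per arm. A gap of 5 patients between two arms would then let 5/39 = 0.13 of even an equal carry-over into that contrast in the realised sample.

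**What added terms could detect at power .80, on the plan's precision.**
- Laboratory DCS v laboratory placebo, all arms (48 v 48): 6.59 × √(39/48) = 5.9 points.
- The same within the placebo arm (12 v 12): 6.59 × √(39/12) = 11.9 points.
- Tailored-v-placebo by laboratory-drug interaction (four cells of 12): 6.59 × √[(4/12)/(2/39)] = 16.8 points.

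If 6.59 referred instead to a 78 v 78 comparison, the first and third figures would rise to 6.59 × √(78/48) = 8.4 and 6.59 × √[(4/12)/(2/78)] = 23.8 points.

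**Leaving out laboratory-DCS participants.** 156 − 48 = 108, or 27 per arm. The standard error of a contrast rises from 2.35 to 2.35 × √(39/27) = 2.83. The change between the two analyses has a standard error of about √(2.83² − 2.35²) = 1.6 points. A placebo-only carry-over of 3 to 6 points, assumed for illustration, would shift the contrast by 0.31 × 3 = 0.9 to 0.31 × 6 = 1.8 points, which could not be told from noise.

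**The case against.** The strongest objection is that crossing is itself the protection. Every arm expects the same 12 of 39, so an equal carry-over drops out of every contrast without any adjustment. This stands. What remains needs an effect of one pill, given with extinction of a lamp-colour fear, that reaches social anxiety weeks of assessments later and differs by arm. No figure in the documents supports that. Table 3 lists the experiment under Screening, and speech exposures start only in session 2, so the documents do not show that the dose falls close to the first exposure. If the promised balance failed, the clause on unbalanced factors could also bring the factor in. The case for a change therefore rests on completeness and low cost, not on demonstrated bias.

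A reader might infer more than the documents support in two ways:

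- **That carry-over can be neither removed nor detected.** The design removes an equal carry-over in expectation. Because the assignment is randomised, with tables prepared in advance, both its main effect and its interaction can be estimated. The plan omits the analysis; the design does not prevent it.
- **That blocks of 4 or 12 cannot balance eight combinations.** This would follow only if a single list generated both assignments, which the plan does not say. Separate clinical lists for laboratory-DCS, laboratory-placebo and non-participating patients, in blocks of 4, 8 or 12, would balance all eight cells. At most, the mechanism is not described.

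It is also fair to object that a main-effect term does not correct arm-specific carry-over, and that the analyses aimed at it are weak. That stands, and it limits how their results may be read.

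**Conclusion.** The omission is real and its consequence is small on present evidence. An expected 12 of 39 patients per arm will have had laboratory DCS, and no stated analysis examines whether that affects clinical outcome. Under the intended balance the arm contrasts are not biased by an equal carry-over. Bias needs a carry-over that differs by arm, at 0.31 of that difference, or a chance imbalance, and the documents size neither. The counts assume equal allocation and achieved crossing. The detectable differences assume that 6.59 points is the precision of a 39 v 39 contrast.

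Naming the factor in the model is still worthwhile. It respects the groups the trial randomises, takes out chance imbalance in the laboratory factor, including imbalance from optional participation, and lets an overall laboratory-DCS effect be seen about as well as a primary contrast (5.9 against 6.59 points). It is a minor, optional-level improvement.

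**What to change.** In Data Analysis, add a three-level laboratory term (not in experiment, laboratory placebo, laboratory DCS) as a predictor of the intercept and growth parameters in the primary model. Only the comparison of laboratory DCS with laboratory placebo is randomised; the not-in-experiment level reflects the participants' own choice and should be read accordingly.

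Pre-specify two descriptive sensitivity results:

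- the three arm contrasts re-estimated without laboratory-DCS participants (about 27 per arm);
- the arm-by-laboratory interaction, as an estimate with its confidence interval.

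State in the plan that both are imprecise and that a non-significant result does not show absence of carry-over.

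**Cost.** Wording in the analysis section; no new patients or data, and no change to treatment. The main term uses two coefficients per growth parameter. A full three-level by four-arm interaction would add 2 × 3 = 6 per growth parameter, which is why it belongs in a sensitivity analysis and not in the primary model. The sensitivity analyses will have low power.

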### **Outcome Analysis**

In order to evaluate whether tailored DCS administration produces superior outcomes to pre-session DCS, post-session DCS, and placebo, we will examine if the dummy variable contrasting tailored DCS to the relevant comparison condition is a significant predictor of the intercept. We will alternately "center" the "assessment week" variable at either posttreatment, 1-mo FU, or 3-mo FU to test for significant differences between conditions at each of these time points.

We will also examine a number of possible moderators of the potential superiority of tailored DCS over the comparison conditions (and, secondarily, of the superiority of pre-and post-DCS administration over PBO). We will use the Fournier approach to identify important moderators. This approach uses an algorithmic method to select significant predictors and moderators within each group of potential moderators (e.g., demographics, clinical and personality characteristics). These selected moderators are then combined in a final analysis, which identifies moderators that are significant over and above the other potential moderators. This approach strikes a balance between testing each moderator separately (which substantially increases Type I error due to the multiple tests) and testing all moderators simultaneously (which may substantially increase the likelihood of Type II error).

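### Randomisation is blocked by site, but the continuous-outcome model does not name site and the covariate rules would practically never admit it; the effect is very small and without bias

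*Combined protocol and SAP*

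**What the plan says.** Participants gives 156 patients recruited at three sites. On allocation, Screening and Randomization says "Randomization will occur by site using variable-sized permuted block randomization (block sizes varying from 4 to 12". The same section adds "The statistician will check the balance of randomization to control for any unbalanced factors".

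Data Analysis describes the model for the continuous outcomes. On time: "We will use a piecewise growth curve model, separately modeling change over time during treatment and follow-up". On levels, assessments are nested within individuals, "which will be nested within treatment cohort, thereby appropriately accounting for correlated scores within cohorts". The arms enter "by including 3 dummy coded variables as predictors of the growth curve parameters". Site is neither a fixed effect nor a level, and it is not mentioned in Outcome Analysis or Power analysis. The general covariate rule is that "any variables that differ among groups will be used as covariates in the final analyses".

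Outcome Analysis tests the arm contrasts on the intercept, re-centring the time "variable at either posttreatment, 1-mo FU, or 3-mo FU to test for significant differences between conditions at each of these time points".

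**The concern.** A factor that restricts the randomisation is normally included in the analysis, so that the reported standard error reflects the design. Here both routes by which a covariate can enter depend on an observed difference between arms. Blocking within site is there to prevent such a difference for site. The rule therefore tends to leave out the one factor that structures the allocation, and to admit only factors that became unbalanced by chance.

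What is at stake is limited. If site affects outcome and is left out, its variance stays in the error terms although the allocation is already balanced for it. The standard error is then a little too wide and the test a little conservative.

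**Working it through.** **The plan's own figure.** Power analysis gives a detectable d of .296 (6.59 LSAS points) at power .80. It rests on variances and covariances that are not printed, and alpha is not stated, so it cannot be rebuilt. Nothing below depends on it except one conversion to LSAS points.

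**Step 1: could an imbalance rule bring site in?** Take equal allocation and blocks of 4, 8 or 12. Complete blocks contribute no difference. The last, incomplete block at a site holds at most 12/4 = 3 patients per arm, so arms at one site differ by at most 3. With 52 patients per site (156/3), a worst split is 14, 14, 13, 11 against 13 expected. If all three sites are that uneven with arm totals still equal (39 each), chi-square = 3 × (1² + 1² + 0² + 2²)/13 = 18/13 = 1.38 on (3 − 1)(4 − 1) = 6 degrees of freedom, p = .97. The 5% critical value is 12.59. Simulated randomisations, with equal and unequal site sizes, gave lowest p-values of .98 to .99 and a largest within-site difference of 3.

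**Step 2: effect on the standard error at one time point.** Assumptions: total variance 1; site share 2, 5 or 10%; cohort share 0 or 5%; cohorts of 5 within one site (Therapy Procedures gives groups of 4-6); arms mixed within cohorts; sites 52/52/52 or 70/50/36; 1,000 allocations per setting. The standard error is the square root of the arm element of (X′V⁻¹X)⁻¹. Without site, X holds the arms and V carries the site plus cohort share as within-cohort covariance. With site, X also holds two site indicators and V carries the cohort share only. Power after adjustment is Φ((1.960 + 0.842) × ratio − 1.960), at an assumed two-sided 5%.

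| Site share | SE without / with site | Power .80 becomes |
|---|---|---|
| 2% | 1.0036-1.0054 | .803-.804 |
| 5% | 1.0084-1.0128 | .807-.810 |
| 10% | 1.0150-1.0222 | .812-.817 |

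The higher ratios belong to a zero cohort share. The mean shift in the contrast from omitting site was at most .001 SD.

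**Step 3: the full piecewise growth model.** REML fits to 1,200 simulated trials in each of five scenarios, no true arm effect, seven assessments at assumed times with five observed. The simulated data also carried an assumed laboratory effect (zero in the null scenario), which is not part of this point.

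- Reported SE without / with site: 1.003-1.004 (site 2%, cohort 5%), 1.006-1.009 (site 5%, cohort 5%), 1.010-1.014 (site 5%, cohort 0).
- Empirical SE without / with site: 0.998-1.003.
- Type I error: 4.3-5.6% without site, 4.6-5.7% with it. The Monte Carlo SE is √(.05 × .95/1200) = 0.6 points, so these ranges cannot be told apart.
- Absolute bias: at most .015 SD in any model (Monte Carlo SE about .006).

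On the plan's scale, 1.4% of the detectable 6.59 LSAS points is 0.014 × 6.59 = 0.09 points.

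**Step 4: if the cohort effect absorbed no site variance.** With no cohort level and site share f, the ratio is 1/√(1 − f), and the true alpha is 2(1 − Φ(1.960/√(1 − f))). For f of 2 to 10%, the ratio is 1.010-1.054, alpha is .048-.039, and power .80 would become .81-.84 after adjustment. This is larger, but still conservative and still small.

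**The case against.** The strongest reply is that there is almost nothing to repair. The contrasts are unbiased, type I error is near nominal, and the empirical standard error does not measurably change. The planned cohort effect probably takes up most of the site variance already. All of this stands, and it is why the point is minor.

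A second reply is that the document is a design paper and never says that its covariate list is closed. That is fair: silence is not exclusion. But the only covariate rules given for the arm comparison are conditional on imbalance, so the plan leaves the handling of site open.

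A reader might make three stronger inferences that the documents do not support.

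- That blocking makes it impossible for site to enter. Neither rule gives a test or threshold, so a literal reading could admit site on a difference of 1 to 3 patients. What blocking all but prevents is a testable imbalance.
- That leaving site out biases the contrasts or inflates false positives. The calculations show no bias, and any departure expected from omitting site is conservative.
- That laboratory assignment must be added too, because "The conditions of the fear extinction experiment will be equally distributed across the four clinical trial conditions". No passage gives an effect of the single laboratory dose on the clinical outcomes. Participation is optional, so a not-in-experiment level would be self-selected. Nor is the point needed for the response and remission models, where a covariate would change the conditional odds ratio.

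**Conclusion.** The point holds as a small one. Site structures the randomisation, the continuous-outcome model does not name it, and the stated covariate rules would practically never bring it in. The cost is a reported standard error about 0.3-1.4% too wide at a site share of 2-5%, and about 2% at 10%, with no bias and hardly any change in real precision.

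This rests on assumed variance shares, equal allocation in blocks of 4, 8 or 12, arms mixed within cohorts, and each treatment cohort lying within one site. The last follows naturally from groups that meet in person, but the documents do not say it, nor that a treatment cohort is the therapy group of 4-6. No trial conclusion is under threat; this is a nice-to-have change.

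**What to change.** In Data Analysis, state that the multilevel models for the continuous outcomes include site (three levels) as a fixed effect whatever the balance check shows, as a predictor of the same growth parameters as the arm dummies under whichever time form is selected, with the cohort random effect kept. Site needs to act on the slopes as well as the intercept. On the intercept alone it would be one constant shift from baseline onward and would not adjust for site differences that develop during treatment or follow-up.

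The cost is one sentence and, for a piecewise linear form, 2 × 3 = 6 degrees of freedom (two site indicators on the intercept, treatment slope and follow-up slope). If site has no effect at all, the reported standard error widens by only 0.04-0.13%. No change to the sample, the randomisation or the assessments is needed.
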